4	210615	
● 3.2, 5.2: Removed references to Rey subtests from cognitive battery as they are not needed for grant milestones.● 4.0 Study Intervention(s)/Investigational Agent(s): Removed description of unused Starstim device system, updated description of Taskflow device system.● Raised cap on recruitment in order to meet goal of 30 completed participants
○ 5.1, 10.0: FROM “up to 40” TO “up to 250”● Lengthened treatment window to allow protocol to be more compatible with participants’ busy schedules
○ 5.2: Separate Days 2, 8, and 14 into 2 visits each○ 5.2: Change sentences to lengthen window of initial 14 visits from 30 days to two months○ 5.2: Change sentences to lengthen treatment window 2 weeks for each of the 5 tDCS sessions○ 5.3: Change anticipated study duration FROM 2.5 months TO 2.5-4 months.	Yes

PROTOCOL TITLE: Combining Neuro-Imaging and Non-Invasive Brain Stimulation for

Clinical Intervention in Opioid Use Disorder

VERSION DATE: 2022-02-11

		
 Changed exclusion in order to more accurately represent the MAT population 
 8.2: FROM “any stimulant use in the past 30 days” TO “stimulant use greater than 10 days in the 30 days prior to enrollment” Changed compensation distribution (but keep total amount the same): 
 11.4: Increased tDCS visit compensation for each of the 10 tDCS visits FROM \$10 TO \$15 11.4: Decreased Follow-up 2 visit compensation FROM \$100 TO \$50 	
3	200217	
 Replaced all references of “WAIS-WISC” with “WAIS” for simplicity “Abbreviations”: Replaced reference to MINI Version 6 with MINI Version 7. 5.0: Specified that WAIS and D-KEFS will be administered on the digital platform Q-Interactive. 5.2: Replaced “reversal learning task” with “executive functioning tasks” Added locations for study visits Section 22: Clarified Multi-Site section Section 9.1: Checked “None of the above” Added language to accommodate a flexible schedule of events Removed Rey Visual Memory Test Corrected minor errors and formatting errors 	No

PROTOCOL TITLE: Combining Neuro-Imaging and Non-Invasive Brain Stimulation for Clinical Intervention in Opioid Use Disorder

VERSION DATE: 2022-02-11

ABBREVIATIONS/DEFINITIONS

- DLPFC - Dorsolateral Prefrontal Cortex
- NAcc - Nucleus accumbens
- FC - Functional connectivity
- OUD - Opioid use disorder
- fMRI - Functional magnetic resonance imaging
- tDCS - Transcranial direct current stimulation
- CMRR - Center for magnetic resonance research
- HCP - Human Connectome Project
- MOUD - Medications for opioid use disorder
- MINI - Mini International Neuropsychiatric Interview, Version 6
- TLFB - Timeline Follow Back

PROTOCOL TITLE: Combining Neuro-Imaging and Non-Invasive Brain Stimulation for Clinical Intervention in Opioid Use Disorder

VERSION DATE: 2022-02-11

1.0 Objectives

1.1 Purpose: The overarching goal of this project is to expand the traditional expertise in non-invasive neuromodulation at the University of Minnesota towards developing novel paired-neuromodulation approaches using tDCS for new addiction treatments that support long-term abstinence. This study will allow us to investigate whether the pairing of DLPFC stimulation and cognitive training can enhance FC between DLPFC and NAcc. We have identified higher FC between DLPFC and NAcc in alcoholics that have successfully maintained abstinence for extended periods of time (7 years). This paired-neuromodulation approach can potentially be used as a therapeutic intervention to decrease substance use probability in addiction (e.g. opioid use disorder). The long term goal is to develop new addiction treatments that support long-term abstinence in opioid use disorder. The overall objective of this proposal is to enhance FC between DLPFC and NAcc as a therapeutic intervention to enhance cognition and reduce substance use rates in opioid use disorder.

2.0 Background

2.1 Significance of Research Question/Purpose: More effective interventions for opioid use disorder (OUD) are needed. With more than 115 individuals in the US dying daily from opioid overdose (HHS 2018), the opioid epidemic is a public health emergency. Despite effective medications for opioid use disorder, treatment discontinuation and substance use approaches 50% at one year. The fact that OUD is so difficult to treat may be reflective of extensive neuroplastic changes that induce and maintain the pathological addiction state. Existing treatment programs using medication and/or behavioral modification tools (e.g. 12-step) may not be sufficiently powerful to overcome the mechanisms maintaining this pathological state. We propose a neuroplasticity based intervention approach utilizing transcranial direct current stimulation (tDCS) and cognitive training with tasks selected to functionally target cognition and brain circuits that are impaired in opioid use disorder with the goal of reducing substance use.

2.2 Preliminary Data: Combination of active tDCS and cognitive training increases frontal-striatal resting state functional connectivity (RSFC) and reduces time to relapse in alcohol use disorder. Our neuroimaging studies have identified a key frontal-striatal network associated with treatment outcome: low frontal-striatal RSFC predicts relapse ([name], Stenger, and Fein 2013b; [name], Endres, and Fein 2014) and high frontal-striatal RSFC supports long-term abstinence ([name], Stenger, and Fein 2013a, [c] 2013). These neuroimaging findings highlight the key role of frontal-striatal RSFC in supporting long-term abstinence. In our pilot randomized controlled study of participants with alcohol use disorder (n=11; [name] PI) designed to enhance frontal-striatal RSFC and cognition, 6 subjects who received active tDCS (2mA anode over left DLPFC, cathode over right DLPFC) were compared to 5 subjects who received sham

PROTOCOL TITLE: Combining Neuro-Imaging and Non-Invasive Brain Stimulation for Clinical Intervention in Opioid Use Disorder

VERSION DATE: 2022-02-11

tDCS. Intervention sessions were 46 minutes (13 min tDCS - 20 min off - 13 min tDCS), for five consecutive days (Trojak et al. 2016; Klauss et al. 2014). All participants underwent concurrent cognitive training (Reversal Learning task and BART) during the 46 minute session. Rest fMRI data was collected pre- and post-intervention. We found: significant Group (active vs sham tDCS) x Time interaction in prefrontal-nucleus accumbens (NAcc) RSFC ($F=7.105$, $p=0.026$; eta-square $\eta^2=0.441$), with prefrontal-NAcc RSFC increase in the active tDCS group but not the sham group (Figure 2). Findings suggest active tDCS during cognitive training can increase frontal-striatal RSFC in addiction. Eight-month follow-up showed that those receiving sham+cognitive training had a significantly shorter time to relapse ($M=19$ days, $SD=5.66$; 50% relapse rate) than those who received active tDCS + cognitive training ($M=110$ days, $SD=27.05$; 60% relapse rate) ($p=0.021$). While these are promising findings for alcohol use disorder, the safety, feasibility, and effect of this combined intervention (tDCS+cognitive training) has not been investigated in individuals with OUD.

2.3 Existing Literature: Opioid misuse is an epidemic in the United States. While medications for opioid use disorder (MOUD) are highly effective, approximately 40% of patients receiving them return to opioid use within the first year of treatment. Available treatments are not very effective with very high relapse rates. Chronic opioid use is associated with cognitive impairments that interfere with adaptive behavior needed for successful recovery (Terrett et al. 2017; Mercuri et al. 2016; Verdejo-García and Pérez-García 2007; Baldacchino, Balfour, and Matthews 2015). These cognitive impairments and their underlying neural substrates are promising targets for intervention that can augment MOUD and reduce substance use rates. Evidence suggests that cognitive training can improve cognition in individuals with opioid addiction, strengthen neural networks mediating cognition (Ramsay, Nienow, and MacDonald 2017; Haut, [name], and MacDonald 2010; Zhang et al. 2015), and improve treatment outcome (Rezapour et al. 2017). However, cognitive training is effort intensive, has small effect sizes and may have limited durability. The primary objective of this study is to test whether transcranial direct current stimulation (tDCS) can be used to boost the effectiveness of cognitive training in enhancing NAcc-frontal functional connectivity and cognition in opioid addiction to improve MOUD treatment outcome. Transcranial direct current stimulation (tDCS) is a non-invasive brain stimulation technique that can modulate brain connectivity. DLPFC stimulation may increase input to NAcc to facilitate proper selection of goal-directed behavior and may also decrease craving in individuals with substance use disorder (Boggio et al. 2008).

3.0 Study Endpoints/Events/Outcomes

3.1 Primary Endpoint/Event/Outcome: In a double-blind randomized design, up to 250 individuals with a current opioid use disorder (OUD) diagnosis, age 18-60 years, enrolled in a methadone or buprenorphine treatment program and

PROTOCOL TITLE: Combining Neuro-Imaging and Non-Invasive Brain Stimulation for Clinical Intervention in Opioid Use Disorder

VERSION DATE: 2022-02-11

clinically stable will be recruited. We will recruit individuals who have been treatment with methadone or buprenorphine for at least 2 months. Patients will receive 10 sessions (2 5-day blocks of 46-minute daily tDCS intervention) of either (i) transcranial direct current stimulation (tDCS) to PFC or (ii) sham-tDCS. All subjects will perform cognitive training during tDCS intervention (active or sham) to prime the engagement of the NAcc-PFC brain circuit. Rest fMRI will be collected pre-intervention, after 5 sessions, and post-intervention. Follow-up interviews will be conducted 1- and 2-months after intervention completion to assess cognition, assess behavior, and query substance use. Dependent variables will be (i) change in NAcc-PFC FC across intervention imaging sessions, (ii) change in cognitive performance across intervention sessions, and (iii) substance use status 2 months after study participation. The Specific Aims are to determine if the intervention: (A1) is feasible and safe in individuals with OUD, (A2) induces circuit-based target engagement (an NIH funding requirement), (A3) induces cognitive performance changes, and (A4) is related to substance use status 2 months after study.

To evaluate feasibility (A1), withdrawal and retention policies are described in Section 12.0. To evaluate safety (A1), we will use the Treatment Side Effects Questionnaire to record intervention side effects. Based on our alcohol tDCS study and studies from other research groups, we hypothesize that the intervention will be feasible and safe.

To evaluate circuit-based target engagement (A2) we will compare brain activation change (from pre-intervention to post-intervention) between active tDCS and sham groups. We hypothesize that the active tDCS group will have a larger increase in brain circuit engagement than the sham group.

To evaluate cognitive performance changes (A3), we will compare cognitive performance change from pre-intervention to post-intervention) between active tDCS and sham groups. We hypothesize that the active tDCS group will have a larger improvement in cognitive performance than the sham group.

To evaluate substance use status during participation and 1- and 2-months later (A4), we will administer the Timeline Follow Back(Sobell and Sobell 1996) questionnaire, assess the number of days of opioid use, and amount at peak use at follow-up (1- and 2-months later). We will also collect saliva/urine samples as often as every week. Based on our alcohol pilot study and literature on the effect of tDCS in other addictions (Lupi et al. 2017; Batista et al. 2015), we hypothesize that the active tDCS group will have lower followup substance use rates and longer abstinence periods than the sham group.

3.2 Secondary Endpoint(s)/Event(s)/Outcome(s): To determine generalization and durability of cognitive training, patients will be asked to complete the following tasks at pre-intervention, post-intervention, 1-month follow-up and 2-

PROTOCOL TITLE: Combining Neuro-Imaging and Non-Invasive Brain Stimulation for Clinical Intervention in Opioid Use Disorder

VERSION DATE: 2022-02-11

month follow-up to examine generalization and durability effects of training: D-KEFS Trail Making Test, D-KEFS Verbal Fluency, D-KEFS Color Word, Digit-Span (WAIS-WISC), Digit Symbol (WAIS-WISC).

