Participants who consent to the study and meet study criteria as per the screening evaluation will be asked to participate in up to 17 study visits over a period of up to two months. This time period includes 10 tDCS sessions over a period of up to 5 weeks.

Participants will also be asked to be available for in-person 1- and 2-month follow-up visits after intervention completion to query substance use and complete cognitive tasks. All sessions will be coordinated with participants' visits to the clinic to minimize burden.

VISIT ONE/Screening Visit: After the participant has agreed to be in the study and signed the consent, the participant will be interviewed by a research staff member from the University of Minnesota and asked questions about the participant's health history and clinical symptoms. Females who could potentially be pregnant will be tested for pregnancy and, if positive, will not be allowed to participate. If testing is refused, participation will not be allowed. If eligible, the participant will complete the Timeline Follow Back (TLFB) and other paper questionnaires reporting opioid use and craving levels. Participants will complete baseline measures for: D-KEFS Trail Making Test, D-KEFS Verbal Fluency, D-KEFS

PROTOCOL TITLE: Combining Neuro-Imaging and Non-Invasive Brain Stimulation for Clinical Intervention in Opioid Use Disorder

VERSION DATE: 2022-02-11

Color Word, Digit-Span (WAIS-WISC). The participant will then be asked to complete a series of questionnaires that assess behavior, personality and substance use. Day 1 assessments will take about 2 hours total. After consent and after the participant acknowledges full understanding of the intervention, the participant will be randomly assigned (with 50% chance) to receive either active tDCS or sham tDCS while the participant performs the reversal learning task (see description of intervention under day 3).

VISIT 2-3/PRE-INTERVENTION: The participant will undergo a pre-intervention assessment, lasting about 2 hours. During the assessment, participants will complete a series of questionnaires that assess opioid use and craving levels, behavior, personality and substance use.

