8.0 Study Population

8.1 Inclusion Criteria: Participants will have a current diagnosis of OUD, be age 18-60 years, be enrolled in a methadone or buprenorphine treatment program in Hennepin Healthcare and be clinically stable. We will recruit individuals who have been in treatment with methadone or buprenorphine for at least 2 months. Inclusion criteria: (i) ability to provide written consent and comply with study procedures; (ii) meet the Diagnostic and Statistical Manual of Mental Disorders (DSM-V) diagnostic criteria for OUD. Subjects may have current comorbid drug use, but their primary substance use disorder diagnosis needs to be based on opioid use. Subjects must have the intention to remain in the methadone or buprenorphine treatment program until the end of the intervention portion of the study. Vulnerable populations will not be included.

8.2 Exclusion Criteria: Any medical condition or treatment with neurological sequelae (i.e. stroke, tumor, loss of consciousness>30 min, HIV); (ii) a head injury resulting in a skull fracture or a loss of consciousness exceeding 30 minutes (i.e., moderate or severe TBI); (iii) any contraindications for tDCS or MRI scanning (tDCS contraindication: actively receiving treatment for seizures or epilepsy; MRI contraindications; metal implants, pacemakers or any other implanted electrical device, injury with metal, braces, dental implants, non-removable body piercings, pregnancy, breathing or moving disorder); (iv) current active psychosis or mania; (v) presence of a condition that would render study measures difficult or impossible to administer or interpret (e.g. current mania, active psychosis); (vi) age outside the range of 18 to 60; (vii) primary current substance use disorder diagnosis on a substance other than opioid except for caffeine or nicotine; (viii) have current significant stimulant use (stimulant use greater than 10 days in the 30 days prior to enrollment) (ix) history of ECT or cortical energy exposure within the past 12 months, including participation in any other neuromodulation studies, (x) prisoners. Nicotine use will be recorded.

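### Aim A4 compares substance use at follow-up with no stated adjustment for the use recorded at Visit 1, which costs precision and leaves a trial of about 30 completers open to chance baseline imbalance

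*Combined protocol and SAP*

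**What the plan says.** Section 3.1 lists three dependent variables. Two are changes: "i) change in NAcc-PFC FC across intervention imaging sessions" and "ii) change in cognitive performance across intervention sessions". The third is a follow-up value: "substance use status 2 months after study participation". For A4 the section adds that staff will administer the TLFB and "assess the number of days of opioid use, and amount at peak use at follow-up (1- and 2-months later"). It also covers use during participation and saliva or urine samples as often as weekly. The hypothesis is that "the active tDCS group will have lower followup substance use rates and longer abstinence periods than the sham group".

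Entry use is recorded. Under Visit One, section 5.2 says: "If eligible, the participant will complete the Timeline Follow Back (TLFB) and other paper questionnaires reporting opioid use and craving levels". No look-back window is given.

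Entry use can vary. Sections 8.1 and 8.2 require clinical stability and at least 2 months on methadone or buprenorphine, but set no opioid-abstinence criterion. Section 8.1 adds that "Subjects may have current comorbid drug use", and section 8.2 excludes stimulant use only above 10 of the prior 30 days.

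Randomisation (section 5.2) uses permuted blocks of 4 with no stratification factor. Section 15.3 plans a before/after mixed model for FC and craving, a repeated measures analysis of the 1- and 2-month data with no outcome named, and a log-rank test with no covariate or stratum. Section 12.2 plans telephone contact to learn the substance use status of people who withdraw after receiving tDCS.

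**The concern.** A participant who was using at entry and is using to the same extent at 2 months counts in A4 in the same way as one who has returned to use. Entry use is a plausible predictor of later use and is measured with the same instrument, so leaving it out has two costs. The arm comparison carries variance that could be removed. And in the one trial that is run, a chance excess of users in one arm at entry moves the A4 estimate in that direction. A4 carries a directional hypothesis under the primary endpoint, so the sign of this result is likely to be read as a signal for later work.

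**Working it through.** The plan gives no power, alpha or SD for A4 (section 15.2 says a power analysis does not apply), so there is no stated figure to reproduce.

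**Inputs**
- Completers: 30, from the amendment log entry that raised the recruitment cap. An even split gives n = 15 per arm.
- Upper bound: 250, the consent cap in section 10.1, or 125 per arm if all were analysed.
- Baseline/follow-up correlation ρ: not in the documents. Assumed 0.2 to 0.7.
- Two-sided alpha of 0.05 and normal outcomes: assumed.

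**Chance imbalance at baseline**
- Standard error of the arm difference in SD units = √(2/n). For n = 15, √(2/15) = 0.365.
- P(gap above 0.5 SD, either direction) = P(|Z| > 0.5/0.365) = P(|Z| > 1.37) = 0.171.
- At 30 per arm, √(2/30) = 0.258 and the probability is 0.053. At 125 per arm, √(2/125) = 0.126 and it is below 0.01%.

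**What carries over, and what adjustment gains**

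The shift in the unadjusted contrast is ρ × gap. Adjustment multiplies the residual variance by 1 − ρ², which is equivalent to 30/(1 − ρ²) completers.

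| Assumed ρ | Shift from a 0.5 SD gap | Variance removed (ρ²) | Equivalent completers |
|---|---|---|---|
| 0.2 | 0.10 SD | 4% | 31 |
| 0.3 | 0.15 SD | 9% | 33 |
| 0.5 | 0.25 SD | 25% | 40 |
| 0.7 | 0.35 SD | 49% | 59 |

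**Simulation** (40,000 trials per scenario, 15 per arm)
- With no true effect, unadjusted type I error is about 0.05 over all trials. Among trials with a baseline gap above 0.5 SD it is 0.077, 0.115 and 0.177 at ρ = 0.3, 0.5 and 0.7. With ANCOVA it is 0.051, 0.047 and 0.057.
- For an illustrative 0.8 SD effect, unadjusted power is about 0.56. ANCOVA gives 0.59, 0.67 and 0.83 at the same three correlations. A change score gives 0.43, 0.56 and 0.78, so a covariate is the better choice.

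**The case against.** **Section 15 is silent, not opposed.** A reader might infer that the plan has chosen a raw comparison and rejected the baseline. It has not. Section 15.3 names no substance-use variable and assigns A4 no model, so the entry value is omitted. The omission still matters, because it leaves the A4 model to be chosen after the data are seen.

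**Randomisation protects the comparison.** This stands. The unadjusted test holds its size on average, and only the share ρ of any imbalance carries over. It would be wrong to say that baseline differences pass through in full or that the test is invalid. The cost is lost precision and a shift conditional on the imbalance that occurs.

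**Day counts are kept.** A reader might take status to mean yes/no and conclude that day counts are thrown away, or judge A4 by the power of a two-proportion test. The documents do not support this. Status is never defined as binary, and section 3.1 lists days of opioid use and peak amount as A4 measures.

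**A4 is more than a 2-month level.** This is also fair. It includes abstinence periods, presumably the target of the log-rank test, and use during participation. That test has no baseline term either, and no event or time origin is given for someone using at entry.

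**The gain may be small.** The sentence on comorbid use concerns drugs other than opioids and does not show how common opioid use is at entry. In a clinically stable sample many participants may report near-zero days. The baseline would then have little spread, and the normal-theory figures would overstate the benefit.

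**This is a declared pilot with a cap of 250.** The cap limits consents and is not an analysis target. With 250 analysed, large imbalances would be negligible, so the size of this point rests on the 30-completer goal.

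**Conclusion.** The point holds as a gap in specification. A4 is framed as use at follow-up, the matching entry measure is collected, and no planned analysis uses it. At about 15 completers per arm, roughly one trial in six (17%) would have a baseline gap above 0.5 SD, shifting the A4 contrast by 0.10 to 0.35 SD for a gap of exactly 0.5 SD and ρ from 0.2 to 0.7. Adjustment is worth between 1 and 29 extra completers over that range (31 − 30 to 59 − 30). These figures assume an even split of 30 completers, a correlation the documents do not give, and normal outcomes. Day counts are likely to be skewed with many zeros, so the figures are indicative only. The documents do not support a claim that the unadjusted comparison is biased on average.

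**What to change.** In sections 3.1 and 15.3:
- State that the A4 comparison of opioid-use days is percent of days with use in a fixed TLFB window, active versus sham, adjusted for the Visit 1 TLFB value. Use the same look-back at Visit 1 and at follow-up.
- Name one prespecified model suited to skewed, zero-heavy data, for example ANCOVA on ranks. Do not substitute a change score.
- Keep substance use status as a reported A4 outcome, and define it. Include status obtained by telephone from people who withdraw, and analyse all randomised participants with data, adjusted for or stratified by Visit 1 use where feasible. A TLFB window before the 2-month visit may not be obtainable from people reached only by telephone, so status should not be dropped in its favour.
- Stratify the log-rank test by use at entry, and define its event and time origin for participants who are using at entry.
- State the number of completers the analysis expects in the current text.

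The cost is wording. No new visit or instrument is needed, provided the Visit 1 TLFB covers the chosen look-back, which should be checked because section 5.2 does not give it. The change should be made before outcomes are examined by arm.
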